The analyses of the secondary rate endpoints will use the same methods as the conservative CLBR and the analysis of secondary time-to-event variables will use the similar methods as the optimal CLBR, which are intended to provide additional characterization of the treatment effect.

Number of oocytes retrieved will be summarized and compared basing on analysis of variance (ANOVA) including treatment and center as factors. The treatment difference and the two-sided 95% confidence interval will be reported.

Furthermore, univariate/multivariate logistic or cox regression analysis will be performed to evaluate the dependence of Age (≤ 35 or > 35 years), AFC, AMH, number of oocytes retrieved, number of usable embryos, times of embryo transfer, and BMI in relation to pregnancy rate or CLBR.

Table X Schedule of Assessments

Procedure Visit	Screening/Baseline	Gn Initiation	Triggering Day	Oocytes pick up	Embryo Transfer		HCG Test	Clinical pregnancy assessment	Ongoing Pregnancy (fresh cycle)	Live Birth	End of Observation	2 years Follow up Visit
					fresh cycle	FET						
Demography	x											
Medical history	x											
Inclusion and exclusion criteria	x											
Signed informed consent form	x											
Physical examination and vital signs	x											
Clinical and gynecological examination	x											
FSH levels within last 3 months	x											
E ₂ level within last 3 months	x											
AMH*	x											
AFC within last 3 months	x											
Administration of GnRH-a (long protocol group)		x	x									
Administration of Gonal-f® new pen		x	x									
Administration of GnRH-ant (GnRH-ant protocol group)			x									
LH levels		x										
r-LH supplementation if need			x									
HCG trigger			x									
E ₂ level		x										
Oocytes pick up				x								

CELEBRATE Study

MS700623_0020

Procedure Visit	Screening/Baseline	Gn Initiation	Triggering Day	Oocytes pick up	Embryo Transfer		HCG Test	Clinical pregnancy assessment	Ongoing Pregnancy (fresh cycle)	Live Birth	End of Observation	2 years Follow up Visit
					fresh cycle	FET						
Embryo transfer					x	x						
Pregnancy assessment by serum β -hCG test							x					
Clinical Pregnancy assessment by ultrasound scan						x		x				
Ongoing pregnancy									x			
Live birth										x		
Safety												
OHSS			x	x								
AEs		x	x	x	x		x	x	x	x		
Concomitant medication		x	x	x	x		x	x	x	x		

* After randomization.

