Both GnRH agonist and GnRH antagonist protocols are widely used in controlled ovarian stimulation (COS); however, there is a persistent debate concerning the reproductive outcomes when comparing the two analogue treatments (Toftager M, 2016). In the most recent Cochrane review, the GnRH antagonist protocol was associated with comparable live birth rate (LBR) and a substantial reduction in the incidence of OHSS when compared to GnRH agonist long protocol in women undergoing ART in none selected population (Hesham G AI,2016).

Comparing with GnRH agonist protocol, the GnRH antagonist protocol is associated with fewer oocytes retrieved, lower OHSS incidence whereas the ongoing pregnancy rate and LBR were similar in supposed normal responders in the recent systematic review and meta-analysis (JS Xiao, 2014). However, the data published in the same year found that among good-prognosis patients, agonist protocol decreased cancellation risk and increased odds of implantation and live birth compared with antagonist protocol using the national surveillance data (D. Grow, 2014).

Overall, there is an ongoing debate regarding the superiority of these two COS protocols in supposed normal responders.

In the other aspect, IVF success has generally been calculated and reported on the basis of LBRs per treatment attempt involving either an intended fresh or frozen-thawed embryo transfer (FET). The continued improvement in reproductive technology has seen an increase in the number of FETs and their associated pregnancy rates. This, combined with an emphasis on reducing multiple pregnancies and increasing single embryo transfers (SETs), means that outcomes per fresh embryo transfer are no longer meaningful to patients and clinicians who want to know their chance of live birth over an entire IVF program. The most appropriate way of reporting this is to estimate the

cumulative chances of success per woman after a number of complete cycles—defined as all fresh and FET attempts resulting from one episode of ovarian stimulation. CLBRs are increasingly proving to be the currency of IVF (DJ. McL 2016).

From fertility counselling perspective, patients undergoing IVF treatments should be informed not only the opportunity of success rate in fresh cycle transfer but also the probability to achieve a live birth after utilization of all cryopreserved embryos.

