8.3.2 Secondary Endpoints

COS and pregnant outcomes, including:

- Number of oocytes retrieved
- Good-quality embryo rate(The Istanbul Consensus1)
- hCG positive rate (in fresh cycle)
- Implantation rate (in fresh cycle)
- Clinical pregnancy rate (in fresh cycle)
- Ongoing pregnancy rate(in fresh cycle)
- Live birth rate(in fresh cycle)
- Cumulative clinical pregnancy rate
- Miscarriage rate(in fresh cycle)
- Ectopic pregnancy rate(in fresh cycle)
- Cycle cancelled rate and reason(in fresh cycle)
- Rate and severity of OHSS(in fresh cycle)
- Time to pregnancy
- Time to live birth

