8.5.2 Analysis of Primary Endpoints

The result of the analysis of the primary endpoint (CLBR) is essential for the non-inferiority claim. The conservative CLBR will be used to test the hypothesis in a confirmatory way.

Definition of the primary endpoint: CLBR with first live birth resulting from one initiated COS cycle.

Numerator is the No. of women got their first live birth, the Denominator is the No. of women who attempt the ovarian stimulation.

There will be two ways to calculate the CLBR:

- The conservative estimate of the cumulative live birth rate, which is based on the assumption that none of the women who do not return for a subsequent embryo transfer would have had a live birth.
- The optimal estimate of the cumulative live birth rate, which is based on the assumption that women who do not return for a subsequent embryo transfer would have had the same live birth rates as those who do return.

Conservative CLBR with the corresponding 95% confidence interval (CI) will be based on binominal distribution. The two treatments will be compared by using Chi-square test for conservative CLBR. The difference between the two treatments and its associated 95% CI based on asymptotic normal distribution will be presented. If the lower-limit of the 95% confidence interval is greater than the non-inferiority limit (-10%), the null hypothesis will be rejected and it would be claimed that GnRH antagonist protocol is non-inferior to GnRH agonist protocol regarding to the cumulative live birth rate.

Optimal CLBR will be analyzed by using Kaplan-Meier product-limit method, the rate and its 95% CI will be provided. For optimal CLBR, the two treatments will be compared using Kaplan-Meier

product-limit estimates, the difference between the two treatments and its associated 95% CI will be also presented.

Number of oocytes retrieved will be summarized and compared basing on analysis of variance (ANOVA) including treatment and center as factors. The treatment difference and the two-sided 95% confidence interval will be reported.

Furthermore, univariate/multivariate logistic or cox regression analysis will be performed to evaluate the dependence of Age (≤ 35 or > 35 years), AFC, AMH, number of oocytes retrieved, number of usable embryos, times of embryo transfer, and BMI in relation to pregnancy rate or CLBR.

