8.5.3 Analysis of Secondary Endpoints

Definition of some important secondary endpoints:

Clinical pregnancy: a pregnancy diagnosed by ultra-sonographic visualization of one or more gestational sacs or definitive clinical signs of pregnancy. It includes ectopic pregnancy. Note: Multiple gestational sacs are counted as one clinical pregnancy.

Clinical pregnancy rate: the number of clinical pregnancies expressed per 100 initiated cycles, aspiration cycles, or embryo transfer cycles. Note: When clinical pregnancy rates are given, the denominator (initiated, aspirated, or embryo transfer cycles) must be specified.

Cumulative clinical pregnancy rate: Numerator is the No. of women got their first clinical pregnancy, the Denominator is the No. of women who attempt the ovarian stimulation.

Live birth rate: Numerator is the No. of women got live birth resulting from fresh cycle (multiple births considered as one live birth), the Denominator is the No. of women who attempt the ovarian stimulation.

Implantation rate: the number of gestational sacs observed divided by the number of embryos transferred.

Ongoing pregnancy: intrauterine pregnancy continued for 12 gestational weeks (detection of presence of gestational sac with fetal heartbeat by transvaginal ultrasound examination in week 12).

Time to pregnancy: time from Gn Initiation to the first clinical pregnancy.

Time to live birth: time from Gn Initiation to the first live birth.

Cancelled cycle: an ART cycle in which ovarian stimulation or monitoring has been carried out with the intention to treat, but which did not proceed to follicular aspiration or, in the case of a thawed embryo, to embryo transfer.

Miscarriage, also known as spontaneous abortion and pregnancy loss, is the natural death of an embryo or fetus before it is able to survive independently

The analysis of the secondary endpoints are intended to provide additional characterization of the treatment effect.

Number, time, percentages and related CIs will also be reported for the following secondary endpoints:

- Number of oocytes retrieved
- Good-quality embryo rate(The Istanbul Consensus1)
- hCG positive rate (in fresh cycle)
- Implantation rate (in fresh cycle)
- Clinical pregnancy rate (in fresh cycle)
- Ongoing pregnancy rate(in fresh cycle)
- Live birth rate(in fresh cycle)
- Cumulative clinical pregnancy rate
- Miscarriage rate(in fresh cycle)
- Ectopic pregnancy rate(in fresh cycle)
- Cycle cancelled rate and reason(in fresh cycle)

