- Rate and severity of OHSS(in fresh cycle)
- Time to pregnancy
- Time to live birth

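### The normal-approximation interval for the difference in CLBR is carried over to every secondary rate, with no small-count method for rare outcomes such as ectopic pregnancy or OHSS by grade

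*Combined protocol and SAP*

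**What the plan says.** Section 8.5.2, repeated in the synopsis under statistical methods, gives three methods for the conservative CLBR:

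- each arm's rate: "Conservative CLBR with the corresponding 95% confidence interval (CI) will be based on binominal distribution";
- the test: "The two treatments will be compared by using Chi-square test for conservative CLBR";
- the difference: "The difference between the two treatments and its associated 95% CI based on asymptotic normal distribution will be presented".

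The synopsis then extends this set to the other rates: "The analyses of the secondary rate endpoints will use the same methods as the conservative CLBR". The list in section 8.3.2 includes "Ectopic pregnancy rate(in fresh cycle)", and the list in section 8.5.3 includes "Rate and severity of OHSS(in fresh cycle)". For the methods, section 8.5.3 adds only this: "Number, time, percentages and related CIs will also be reported for the following secondary endpoints". It names no type of interval and no test.

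No exact, score or continuity-corrected method for small counts appears anywhere. Section 8.5.1 defers to a later analysis plan only for the handling of missing data.

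**The concern.** The normal approximation needs a reasonable number of events in each arm. A CLBR of about 60% provides them; a rare harm may not. With few events, the estimated standard error of the difference can be far too small, and with none it is zero.

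OHSS matters to how this trial will be read. Section 3 cites, for the antagonist protocol, "a substantial reduction in the incidence of OHSS when compared to GnRH agonist long protocol", and section 4.2 makes safety part of the secondary objective. An expected reduction makes unequal rates plausible, and low unequal rates are where this interval does worst. At stake is the uncertainty reported around a harm comparison: an interval of 0 to 0, or one that narrowly excludes zero on four events. The trial is open-label, so a switch of method after the counts are known would be hard to defend.

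**Working it through.** **Inputs from the plan (section 8.1).** CLBR 60% in both arms, margin 10 points, two-sided 95% interval, 80% power, 377 evaluable and 444 randomized per arm, 15% dropout.

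**Assumptions.** Event rates of 0.1% to 2%, because the documents give none. Denominators of 444 and 377 per arm, because none is stated for OHSS or ectopic pregnancy. The asymptotic-normal interval is read as the unpooled (Wald) form. Differences are antagonist minus agonist.

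**The plan's own figure.** n = (1.960 + 0.842)² × 2 × 0.6 × 0.4 / 0.10² = 7.849 × 0.48 / 0.01 = 376.7, so 377. Then 377 / 0.85 = 443.5, so 444. Both reproduce.

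**Zero width.** The interval is d ± 1.96 × √[p1(1−p1)/n + p2(1−p2)/n]. With no events in either arm, d = 0 and the root is 0, so the interval is 0 to 0. For a common true rate p, the probability of this table is (1−p)^(2n):

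| p | 444 per arm | 377 per arm |
|---|---|---|
| 0.2% | 0.998^888 = 16.9% | 22.1% |
| 0.5% | 0.995^888 = 1.2% | 2.3% |
| 1% | 0.99^888 = 0.01% | 0.05% |

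The Newcombe interval for 0/444 versus 0/444 is −0.86 to +0.86 points.

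**Coverage.** The probabilities of all pairs of binomial counts whose interval contains the true difference were summed:

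| True rates | Wald, 444 | Wald, 377 | Newcombe, 444 |
|---|---|---|---|
| 0.1% vs 0.5% | 88.7% | 84.7% | 99.8% |
| 0.2% vs 1.0% | 92.2% | 88.2% | 98.3% |
| 0.5% vs 2.0% | 94.6% | 94.0% | 96.5% |
| 1.0% vs 2.0% | 94.8% | 94.7% | 96.1% |

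With equal rates (0.05% to 3%) and 444 per arm, the lowest Wald coverage is 94.8%. This is partly a technicality: when the true difference is zero, a 0-to-0 interval counts as covering it although it conveys no uncertainty.

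**Chi-square test.** The exact type I error of the uncorrected test at 444 per arm is 0.14% at a 0.1% rate, 1.1% at 0.2%, 4.4% at 0.5% and 4.3% at 1%. The maximum over 0.05% to 3% is 5.01%.

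**One sparse table: 0/444 versus 4/444.**

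- d = −4/444 = −0.90 points. SE = √(0.00901 × 0.99099 / 444) = 0.448 points. Wald: −0.90 ± 1.96 × 0.448 = −1.78 to −0.02.
- Pooled rate 4/888 = 0.00450. z = 0.00901 / √(0.00450 × 0.99550 × 2/444) = 2.004, so p = 0.045.
- Newcombe: the Wilson limits are 0 to 0.858% and 0.351% to 2.293%. Lower limit −0.901 − (2.293 − 0.901) = −2.29. Upper limit −0.901 + √(0.858² + 0.550²) = +0.12.
- Miettinen-Nurminen: at a difference of zero its statistic is 2.004 × √(887/888) = 2.003, above 1.96, so it still excludes zero. Solved numerically, its limits are −2.29 to −0.04.
- Fisher's exact test: p = 0.124.

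So the two score-based intervals agree on the lower limit here but fall on opposite sides of zero at the upper.

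**The case against.** The strongest reply is that little depends on this. The secondary analyses are described as additional characterization, section 8.5.2 reserves confirmatory testing for the conservative CLBR, and section 8.5.3 names no test. All of that stands.

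A reader might infer that the plan will produce false significance for harms. The calculations do not support that: the chi-square test stays at about 5% or below and is very conservative at the rarest rates. Only particular tables, such as 0 versus 4, look significant on thin evidence. The coverage loss also does not mainly create spurious differences. At 0.2% versus 1.0% with 444 per arm, the 7.8% of misses divide into 7.1% where the interval lies too near zero and 0.7% where it lies too far from it. Most of the error understates a real difference.

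A reader might also infer that a harm with no events would be reported with no uncertainty at all. That goes too far. Each arm's interval is to be based on the binomial distribution, which may mean exact; for 0/444 the exact upper limit is 0.83%. Zero width applies only to the difference.

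Finally, the size rests on assumed rates and denominators. With 200 per arm, coverage at 0.5% versus 1.0% would be 85.9%, but the documents state no such denominator. At 444 per arm the same rates give 94.6%.

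What remains is that the carry-over is an explicit rule, it covers endpoints that may be sparse, and nothing in the plan replaces it when they are.

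**Conclusion.** The point holds as a minor one. Followed as written, the plan puts an asymptotic-normal interval around the difference in every secondary rate. That interval degenerates when neither arm has an event and under-covers when rates are very low and unequal. If ectopic pregnancy or an OHSS grade occurs in roughly 0.1% to 0.5% of one arm and up to 1% of the other, coverage can fall to about 85% to 92%. At equal rates with equal arms, or at about 1% to 2% with 444 per arm, the shortfall is negligible. The conclusion assumes the Wald reading, the rates shown, and denominators near the planned arm sizes. The sample size and the primary CLBR comparison are not affected.

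**What to change.** In the synopsis, end the carry-over of the CLBR difference interval to secondary rates. State there and in section 8.5.3 that the between-arm difference in each secondary rate is reported with a score-based 95% interval, either Miettinen-Nurminen or Newcombe, and that for sparse endpoints this interval carries the comparison. State also that the per-arm binomial interval is exact, if that is what is meant.

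Choose one interval in advance, since the two can disagree about zero, as at 0 versus 4. If a p-value is wanted, name one test consistent with the interval; the Miettinen-Nurminen interval has its own score test. Do not pair Newcombe with Fisher's exact test, because they conflict in the tables at issue. For 0 versus 5 of 444, Newcombe gives −2.61 to −0.05 points while Fisher gives p = 0.062. For 1 versus 7, Newcombe gives −3.00 to −0.03 and Fisher p = 0.069.

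The cost is one or two sentences and a standard software option, with no change to sample size or conduct. The downside is somewhat wider intervals for rare events: for 0 versus 4, Newcombe spans 2.29 + 0.12 = 2.41 points against 1.78 − 0.02 = 1.76. The primary CLBR interval can stay as it is.

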4.1 Primary Objectives

To investigate the cumulative live birth rates in infertile women ≤ 38 years old with normal ovarian reserve using GnRH antagonist or agonist protocol for COS in ART treatment

4.2 Secondary Objectives

To investigate the safety and pregnancy outcomes of GnRH antagonist and agonist protocols

[figure not shown]
4.3 Other Objectives

To explore the relationship between the number of oocytes retrieved and number of embryos or times of embryo transfer or CLBR

5 Investigational Plan

5.1 Overall Trial Design and Plan

This is a multicenter prospective study which will observe the cumulative live birth rates (CLBRs) of gonadotrophin-releasing hormone (GnRH) antagonist protocol compared with the standard GnRH agonist long protocol for controlled ovarian stimulation in supposed normal ovarian responders in China. The recruitment period is planned to start on March, 2018 and to last for 2 years, last-subject-out is expected in December 2020.

This study is planned to involve 5 hospitals and recruit 888 female subjects. Relevant data according to study requirements will be recorded in standard case report form (eCRF). When the study initiates, each reproductive center will screen and enroll qualified subjects to enter the treatment. If a subject has entered the study and later discontinues from the treatment cycle, the reason of discontinuing the treatment should be recorded in eCRF.

Each subject will be followed up to 2 years until she has one live birth or all her embryos are used up after one initiated COS, including fresh & frozen-thawed embryo transfers. Subjects who do not obtain live birth but with embryos left for FET in the 2 years follow up will not be analyzed as drop-out cases either and the CLBR for those patients will be calculated and analyzed in appropriate statistical methods.

5.2 Discussion of Trial Design

Both GnRH agonist and GnRH antagonist protocols are widely used in controlled ovarian stimulation (COS); however, there is a persistent debate concerning the reproductive outcomes when comparing the two analogue treatments (Toftager, M 2016). In the most recent Cochrane review, the GnRH antagonist protocol was associated with comparable live birth rate (LBR) and a substantial reduction in the incidence of OHSS when compared to GnRH agonist long protocol in women undergoing ART in none selected population (Hesham G Al-I,2016).

Comparing with GnRH agonist protocol, the GnRH antagonist protocol is associated with fewer oocytes retrieved, lower OHSS incidence whereas the ongoing pregnancy rate and LBR were similar in supposed normal responders in the recent systematic review and meta-analysis (Jin-song Xiao, 2014). However, the data published in the same year found that among good-prognosis patients, agonist protocol decreased cancellation risk and increased odds of implantation and live birth compared with antagonist protocol using the national surveillance data (Grow D, 2014).

Overall, there is an ongoing debate regarding the superiority of these two COS protocols in supposed normal responders.

The retrospective data from Peking University Third Hospital showed that the CLBR was about 50% in unselected population (unpublished data). The CLBR was about 60% with 11-15 oocytes retrieved in a Chinese population from retrospective published data (Jingjuan Ji, 2013).

The latest published data regarding the CLBRs of these two protocols in a prospective study showed comparable results (34.1% in the GnRH-antagonist group vs 31.2% in the GnRH-agonist group) in unselected population (Toftager M, 2017). However, the CLBR in this study was just a secondary endpoint and it is much lower than the data expected in Chinese population.

5.2.1 Inclusion of Special Populations

Not applicable.

5.3 Selection of Trial Population

Only patients meeting all inclusion criteria and no exclusion criteria may be enrolled into the trial as subjects. Prior to performing any trial assessments which is not part of the subject's routine medical care, the investigator will ensure that the subject or the subject's legal representative has provided written informed consent following the procedure described in Section 9.2.

5.3.1 Inclusion Criteria

Eligible patients for this study should meet all of the following inclusion criteria:

1. Infertile women planning to undergo IVF/ICSI cycle using conventional GnRH agonist long protocol or GnRH antagonist protocol
2. Age \leq 38 years old
3. Basal AFC 8~20
4. Basal FSH \leq 10 IU/L
5. Basal E₂ < 200 pmol/L
6. Normal uterus and at least one side of the normal ovary
7. Informed consent form signed
8. Willing to follow the study protocol, and able to complete this study

5.3.2 Exclusion Criteria

Patients are not eligible for this trial if they fulfill any of the following exclusion criteria:

1. Previous IVF/ICSI cycles > 2
2. Severe hydrosalpinx (Ultrasound shows hydrosalpinx > 2cm)
3. Severe endometriosis (Grade III – IV)
4. Polycystic ovarian syndrome (PCOS)
5. History of recurrent miscarriages (> 2 times of miscarriages)
6. Plan to undergo ovarian stimulation for preimplantation genetic diagnosis or preimplantation genetic screening, oocyte donation, and social or medical freezing of oocytes
7. Any major systemic disease that as per Investigator's discretion precludes subject for participation in the study
8. With pregnancy contraindications
9. Alcoholism, drug abuse, drug addiction or patients with uncured sexually transmitted disease

10. According to the judgment of the Investigator, any medical condition or any concomitant surgery/medications that would interfere with evaluation of study medications
11. Simultaneous participation in another clinical study
12. Plan to use urinary gonadotrophin during COS treatment

